Study Design:	
This is a non-randomized, open label, multi-site, single dose, Phase 1/2 study in approximately 50 adults and adolescents with severe SCD. The study will evaluate hematopoietic stem cell (HSC) transplantation (HSCT) using bb1111 (lovotibeglogene autotemcel, also known as LentiGlobin BB305 Drug Product for SCD), an autologous CD34+ cell-enriched population from patients with sickle cell disease that contains hematopoietic stem cells transduced with BB305 lentiviral vector encoding the $\beta^{\text{A-T87Q}}$-globin gene, suspended in cryopreservation solution.
 
Treatment is divided into 4 stages, as follows.
 
Stage 1- Screening and eligibility assessment Subjects will be screened and undergo clinical, imaging, and laboratory assessments for eligibility determination.
 
Stage 2 - Stem cell harvest, drug product manufacture and disposition If subjects are taking hydroxyurea (HU), it must be discontinued at least 30 days prior to stem cell harvest. It may be restarted between completion of the stem cell harvest(s) and admission to the hospital for myeloablation but should be stopped again at least 2 days before initiating myeloablation.
 
For at least 60 days prior to stem cell harvest and continuing through until the start of conditioning, subjects will undergo a transfusion regimen (exchange or simple, as available or needed) to reach a target hemoglobin (Hb) of 10 g/dL prior to mobilization (and 8 to 10 g/dL prior to conditioning; not to exceed 12 g/dL prior to either mobilization or conditioning) and a pre-transfusion target hemoglobin S (HbS) proportion in the blood of < 30% to reduce the risk of SCD-related complications. The last exchange transfusion must occur within 4 days of start of mobilization, and the HbS proportion in the blood must be < 20% after the last exchange transfusion. If a subject experiences an SCD-related crisis within 1 month of the start of mobilization, the transfusion regimen will be adjusted, and mobilization will be postponed until the subject is crisis-free for a period of 1 month. In case of iron overload, subjects should be adequately chelated; however, iron chelation must be discontinued at least 7 days prior to stem cell harvest. It may be restarted between completion of the stem cell harvest(s) and admission to the hospital for myeloablation but should be stopped again at least 7 days before initiating myeloablation.

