	
least 4 VOEs in the 24 months prior to Informed Consent are enrolled and received drug product in Group C.
 
Power calculations were also performed for the key secondary efficacy endpoints of sVOE-CR and Globin Response. Assuming 85% of subjects in Group C with at least 4 VOEs in the 24 months prior to Informed Consent will meet sVOE-CR, 35 subjects will provide more than 99% power to reject the null hypothesis of 50% at 1-sided alpha of 0.025, using the Exact Test per EAST® (Version 6); the success criterion is 69% (24 out of 35) of subjects meeting sVOE-CR, if exactly 35 subjects with at least 4 VOEs in the 24 months prior to Informed Consent are enrolled and receive drug product in Group C. Assuming 70% of subjects will meet Globin Response, 41 subjects will provide approximately 96% power to reject the null hypothesis of 40% at 1-sided alpha of 0.025, using the Exact Test per EAST® (Version 6); the success criterion is 59% (24 out of 41) of subjects meeting Globin Response, if exactly 41 subjects are enrolled and received drug product in Group C.
 
Populations for analysis
 
The following subject populations will be evaluated and used for presentation and analysis of the data:
 
• Intent-to-Treat (ITT) Population: All subjects who initiate any study procedures, beginning with stem cell collection procedures (mobilization/apheresis or bone marrow harvest).• Transplant Population (TP): All subjects who receive drug product.• Transplant Population for VOE (TPVOE): Subset of TP subjects with at least 4 VOEs in the 24 months prior to Informed Consent.• Successful Engraftment Population (SEP): A subset of TP subjects who, following busulfan myeloablation and drug product infusion, successfully engraft with drug product, defined as 3 consecutive absolute neutrophil count (ANC) $\geq 0.5 \times 10^9/L$ laboratory values obtained on different days after the initial post-infusion nadir by Day 43. 
The ITT is the primary population for the analysis of safety, the TPVOE is the primary population for VOE-related endpoints including the primary efficacy endpoint of VOE-CR and the key secondary endpoint of sVOE-CR, the TP is the primary population for the key secondary efficacy endpoint of Globin response, and the other secondary efficacy endpoints and pharmacodynamic endpoints. The SEP will be used to provide supportive data for subjects who engraft.
 
Analysis of the primary efficacy endpoint in Group C
 
The primary endpoint of VOE-CR will be tested against the null hypothesis of 40% using a 1-sided exact binomial test. The number and percentage of subjects reaching the primary endpoint will be presented. The associated 2-sided exact 95% confidence interval will be provided. The primary endpoint will be analyzed in the TPVOE population in Group C subjects.
 
Analysis of the key secondary efficacy endpoints in Group C
 
The key secondary endpoint of sVOE-CR will be tested against the null hypothesis of 50% using a 1-sided exact binomial test. The number and

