6.2.30. Adverse Events

6.2.30.1. Assessments During Study

Monitoring of AEs will be conducted from the signing of informed consent. Adverse events, as defined in [Section 6.2.30.2](#) will be documented from the time informed consent is signed through the following time points for Groups A and B:

- \geq Grade 1 AEs: through 30 days after drug product infusion.
- \geq Grade 2 AEs: through 12 months after drug product infusion.
- All serious adverse events (SAEs), \geq Grade 3 AEs, and drug product-related AEs: through 24 months after drug product infusion.

For Group C, AEs for all subjects (excluding screen failures) will be recorded in the CRFs starting from the time informed consent is signed through the Month 24 Visit. All SAEs (including screen failures) will be reported from the signing of informed consent/assent on the SAE report form. Group C subjects enrolled under Version 7.0 of Protocol HGB-206 will have AEs retrospectively documented to be in accordance with Version 8.0 and Version 9.0 of Protocol HGB-206.

All AEs should be monitored until they are resolved or are clearly determined to be due to a subject's stable or chronic condition or inter-current illness(es). See also [Section 4.5](#) for AE monitoring of subjects who withdraw from the study.

For subjects who withdraw for reasons other than withdrawal of consent, any SAEs open at the time of discontinuation should be followed up until resolution or are determined to be a stable or chronic condition. If withdrawal is before drug product infusion, subjects should remain on study for at least 30 days after any invasive study procedure (e.g., mobilization, liver biopsy) before withdrawal and ongoing AEs should be monitored for the 30-day duration. In the rare case a subject undergoes myeloablation and receives back-up cells instead of bb1111, subject should remain on the study for at least 3 months post-myeloablation and AEs should be followed for the 3-month duration.

If withdrawal is after drug product infusion, subjects will be asked to complete the same assessments as specified in the SOE for Month 24 (Early Termination Visit assessments) and are expected to enroll in the long-term follow-up study.

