7.4.5. Safety Analyses

The safety analyses will include evaluation of the incidence of AEs by Preferred Term and System Organ Class coded using the Medical Dictionary for Regulatory Activities (MedDRA). Adverse events will be summarized for the ITT population for those events that occur from signing of informed consent through the Month 24 visit. All AEs will be listed and summarized for the following time periods: 1) from Informed Consent up to the initiation of the stem cell harvest procedure (first administration of mobilization agent, or bone marrow harvest); 2) from initiation of the stem cell harvest procedure up to start of conditioning; 3) from start of conditioning (approximately D-6) through neutrophil engraftment; 4) from neutrophil engraftment through Month 24 Visit; 5) from the day of drug product infusion (Day 1) through Month 24 Visit; 6) from Informed Consent through Month 24 Visit. All AEs will be listed in by-patient, by-time data listings, including any events that may have occurred after signing Informed Consent but prior to stem cell harvest.

Changes in laboratory parameters over time will be summarized for the ITT population with descriptive statistics, including laboratory shifts tables.

Additional summaries of safety data may be produced, if warranted for further characterizing the safety profile of study subjects.

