3.11. Analysis Visit Windows

All evaluation visits are expected to occur following scheduled evaluation per the protocol. The data used in summaries will be tabulated per the evaluation visit as recorded on the CRF. If the evaluation visit is missing due to early withdrawal or missing visits but there is data from unscheduled or additional visit that is inside an analysis visit window as defined in [Appendix 6.2, Table 12](#), then the data from the unscheduled or additional visit will be used for the analysis visit window in data summaries.

For endpoints that are not Hb fractions, if subjects have multiple unscheduled or additional evaluations within an analysis visit window, the evaluation closest to the target visit date will be used in the summary tabulations. In case of evaluations equidistant to the target visit date within an analysis visit window, results of the earlier evaluation will be used. This applies to all assessments without designated visits.

For Hb fractions, if subjects have multiple unscheduled or additional evaluations within an analysis visit window, the mean of these evaluations will be used in the summary tabulations and the detailed rules can be found in [Section 4.4](#).

Windows for time course distributions of AEs and concomitant medications are based on the following time periods:

- ICF until prior to either initiation of mobilization or bone marrow harvest (ICF to < MB)
- Initiation of mobilization (or bone marrow harvest) until prior to initiation of conditioning (MB to < C)
- Initiation of conditioning until prior to initiation of neutrophil engraftment (NE) (C to < NE)
- Initiation of NE through Month 24 (NE to M24)
- Day 1 (drug product infusion) until prior to initiation of NE (D1 to <NE)
- Day 1 (drug product infusion) through Month 24 (D1 to M24)
- Informed Consent Form through Month 24 (ICF to M24)

Note: initiation of NE is counted as the first date of the 3 consecutive ANC assessments that are $\geq 0.5 \times 10^9/L$ obtained on different days after the initial post-transplant nadir by Day 43.

Windows for time course distributions of clinical laboratory shift tables (shift categories defined by CTCAE grade, Version 4.03) are based on the following time periods:

- Initiation of mobilization (or bone marrow harvest) until prior to initiation of conditioning (MB to < C)
- Initiation of conditioning until prior to initiation of NE (C to < NE)
- Initiation of NE through Month 12 (i.e., Day 365) (NE to M12)

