4.6. Safety Analysis

The safety analyses identified below will be performed on subjects in all 3 Groups in the ITT population or TP, as appropriate. Supportive figures will be provided as needed.

Because the safety profile will be assessed for several different time intervals (see [Section 3.11](#)) there may be subjects in the ITT population who are not eligible for analyses during some of these intervals. For example, if a subject has conditioning-regimen related events and does not receive drug product, that subject would not be considered in the analyses of safety data post-drug product infusion (i.e., Day 1 through Month 24 Visit).

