4.6.1. Adverse Events

AE collection windows for Groups A and B are different than those for Group C, and the details can be found in [Section 1.2.1](#). All AEs will be coded via MedDRA coding system (version 23.0 or higher) and displayed in tables and listings using SOC and PT. The safety analyses will include evaluation of all AEs and of treatment-emergent AEs. The terminology "treatment-emergent" is reserved for events that occur during or after drug product infusion.

Summaries of AEs related to drug product will be based on the investigator's assessment; an assessment of 'Possibly Related', 'Related' or missing (if AE occurred after drug product

infusion) will be considered related to drug product. AEs will be summarized by the time intervals mentioned in [Section 3.11](#). For treatment-emergent AEs, only the following time intervals will be presented: "D1 to <NE" which is from drug product infusion to the latest date prior to initiation of neutrophil engraftment, "NE to M24", and "D1 to M24". The number of subjects "at risk" in each time interval will also be provided in summary tables. Subjects who are lost to follow-up, withdrew from the study, or died prior to the beginning of the time interval will be excluded from the number "at risk" in the time interval.

Summary information (the number and percentage of subjects by SOC and PT, separated by group and by time interval) will be tabulated for:

- All AEs
- Treatment-emergent AEs
- Serious AEs (SAEs)
- Treatment-emergent SAEs
- Grade 3 or higher AEs
- Grade 3 or higher treatment-emergent AEs
- Treatment-emergent AEs related to drug product
- Treatment-emergent SAEs related to drug product
- AEs attributed to SCD
- AEs attributed to SCD post Month 6
- SAEs attributed to SCD
- SAEs attributed to SCD post Month 6
- AEs attributed to cell procurement (bone marrow harvest ^[1] and mobilization/apheresis ^[1])
- Grade 3 or higher AEs onset within 7 days post plerixafor
- AEs attributed to conditioning ^[1]
- AEs attributed to study procedure ^[1]
- AEs from Informed Consent to Month 24 visit by selected subgroups (as specified in [Section 3.8](#) as appropriate), to be presented in two time intervals: "ICF to M24" and "D1 to M24".
- AEs by maximum severity (overall and by selected subgroups)
- Events of interest (search criteria in [Appendix 6.7](#))

^[1] Based on attribution on CRF for events as reported by investigators

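### AEs between consent and the start of stem cell collection are tabulated only in subjects who go on to start collection, so pre-harvest deaths and participation-ending AEs cannot enter those tables

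*Protocol*

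**What the plan says.** ITT has the same definition in the protocol synopsis, Protocol 7.2 and SAP Table 2: "All subjects who initiate any study procedures, beginning with stem cell collection procedures (mobilization/apheresis or bone marrow harvest". Entry requires that collection has begun.

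Protocol 7.4.5 states: "Adverse events will be summarized for the ITT population for those events that occur from signing of informed consent through the Month 24 visit". Its first summary period runs "1) from Informed Consent up to the initiation of the stem cell harvest procedure". SAP 3.11 keeps that period: "ICF until prior to either initiation of mobilization or bone marrow harvest (ICF to < MB". SAP 3.11 also has a window from consent through Month 24.

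SAP 4.6 says the safety analyses are "performed on subjects in all 3 Groups in the ITT population or TP, as appropriate". TP is the narrower of the two sets, because it requires infusion. SAP 4.6.1 adds an at-risk rule for each interval: "Subjects who are lost to follow-up, withdrew from the study, or died prior to the beginning of the time interval will be excluded".

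On data collection in Group C, Protocol 6.2.30.1 says "AEs for all subjects (excluding screen failures) will be recorded in the CRFs starting from the time informed consent is signed". On what happens in this window, the synopsis (Study Design, Stage 2) says "For at least 60 days prior to stem cell harvest and continuing through until the start of conditioning, subjects will undergo a transfusion regimen".

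**The concern.** The event that ends the first AE period is also the event that admits a subject to the analysis set. The table for that period is thus conditioned on having come through it. A consented, eligible subject who dies before collection, or leaves because of an AE, is neither a screen failure nor in ITT.

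The window is not empty of study activity. It contains the transfusion regimen and the withdrawal of hydroxyurea before harvest, and screening may include a liver biopsy. Frequency and severity of AEs and SAEs is a listed safety endpoint, and the sponsor chose to tabulate this period separately. A reader of the clinical study report will take that column as the incidence of pre-harvest events among those who entered the study. What it gives is the incidence among those who stayed long enough to be harvested. The consent-to-Month-24 summary carries the same gap in its pre-harvest part.

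**Working it through.** The plan states no figure to reproduce here. The check is on table membership, followed by a bound from SAP Table 1.

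**Membership**

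- Let S be the start of mobilization or bone marrow harvest. A subject is in ITT only if S occurs. The first AE period runs from consent to just before S.
- If a subject dies in that period, S never occurs, so the subject is not in ITT. Deaths shown in the first period are therefore 0 whatever the true count.
- The same holds for an AE that ends participation before S.
- The at-risk rule in SAP 4.6.1 does not repair this. It removes from an interval those already gone before the interval begins. The first interval begins at consent, so by that rule a subject who dies before harvest is at risk at its start. The ITT restriction removes that subject anyway, and the rule adds nobody from outside ITT.
- SAP 4.6 recognizes that some ITT subjects may be ineligible for certain intervals. It does not address ITT being too narrow for the first one.

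**How many could be affected**

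Inputs from SAP Table 1 and SAP 1.2.1:

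| | A | B1 | B2 | C | Total |
|---|---|---|---|---|---|
| Consented and assigned | 9 | 1 | 3 | 51 | 64 |
| Infused | 7 | 1 | 1 | 36 | 45 |

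- Not infused overall: 64 − 45 = 19.
- All 9 Group A subjects are described as harvested, so the 2 who were not infused are in ITT: 19 − 2 = 17.
- The 2 subjects moved from B2 to C had already started collection, so they are in ITT. If the 36 includes them, Group C has 51 + 2 − 36 = 17 subjects not infused. If it does not, 51 − 36 = 15.
- Not being infused is not the same as leaving before collection. The documents do not say how many of these subjects left before mobilization, or whether the 51 includes screen failures. The number d who consented and never started collection is therefore between 0 and 17.
- Group A was formed retrospectively from subjects who had been harvested, so Table 1 could not show a pre-harvest exit there.

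**What the table would show**

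Suppose d subjects left before harvest because of death or an AE (an assumption). The ITT table shows 0/(64 − d). A table of all 64 would show d/64:

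- d = 1: 0/63 against 1/64 = 1.6%
- d = 3: 0/61 against 3/64 = 4.7%
- d = 5: 0/59 against 5/64 = 7.8%
- d = 17 (extreme bound): 0/47 against 17/64 = 26.6%

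**Illustration for SAE incidence in Group C**

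Assume 51 + 2 = 53 consented, none a screen failure, and a 10% risk in this period among those later mobilized. The planned table shows 10% in every case. The early-leaver counts and risks below are assumed:

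- 5 left early with 40% risk: (48 × 0.10 + 5 × 0.40)/53 = 6.8/53 = 12.8%
- 10 left early with 60% risk: (43 × 0.10 + 10 × 0.60)/53 = 10.3/53 = 19.4%
- 5 left early with no events: (48 × 0.10)/53 = 4.8/53 = 9.1%

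The last line shows that the planned figure can also be too high when subjects leave for other reasons.

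**The case against.** The strongest reply is that these events will be reported elsewhere. SAP 4.1 plans a disposition summary of everyone who signs the main consent, and summarizes reasons for premature discontinuation without restricting that to ITT. Protocol 7.4.5 commits to by-patient AE listings that include events before harvest, and SAP 4.6.1 lists deaths, SAEs and AEs leading to discontinuation. With at most 17 subjects in question, listings are readable. All of this stands. A reader might infer that pre-harvest deaths would vanish from the report, and the documents do not support that. What they lack is AE incidence by SOC and preferred term with a denominator that includes these subjects. Both documents also allow further safety summaries or other populations, but as options, not commitments.

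Four other stronger readings also fail:

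- **That 15 to 17 subjects left before mobilization.** Those counts are of subjects not infused. Subjects who stop after collection, for example for inadequate cells or product that cannot be released, are in ITT.
- **That all AE incidence in this period is understated.** Only deaths and AE-driven exits have a certain direction. Early leavers also have less time at risk.
- **That the transfusion-reaction rate in Protocol 1.1 gives the expected size.** That figure concerns chronic transfusion therapy, not the pre-harvest regimen.
- **That the safety objective expressly covers pre-harvest transfusion.** The objective is the safety of treatment with bb1111. The relevance of this window rests on the general AE/SAE endpoint and on the sponsor's decision to tabulate it.

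It is also fair to say that treatment-emergent tables begin at infusion, and that events from plerixafor, harvest and conditioning arise after ITT entry. Those tables are unaffected.

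**Conclusion.** The point holds for the AE tables that begin at consent. In the consent-to-harvest summary, and in the pre-harvest part of the consent-to-Month-24 summary, deaths and participation-ending AEs before harvest are excluded by the definition of the population. This follows from the wording and needs no assumption.

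The size is unknown. Between 0 and 17 Group C subjects could be affected. If none left before collection, no figure changes. The 12.8% and 19.4% results are illustrations under assumed risks, not estimates. No efficacy result, sample size or treatment-emergent safety table is touched. The correction is worth making because a stated rule produces a selected incidence and the data needed to avoid that are already collected from consent.

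**What to change.** In Protocol 7.4.5 and SAP 4.6 and 4.6.1:

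- Summarize the consent-to-harvest and consent-to-Month-24 periods in all consented subjects who are not screen failures. Add this set to SAP Tables 2 and 3, and show the number at risk at consent.
- Report deaths and SAEs in screen failures separately. Protocol 4.6 counts anyone unable to finish screening assessments as a screen failure, and Protocol Table 2 places the transfusion regimen and any liver biopsy in the screening column. Without this line the new set would still miss some early exits. Only SAEs are collected for screen failures, so full AE incidence cannot be given for them.
- Keep ITT for periods that start at mobilization or harvest, and TP for periods that start at infusion.

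The cost is one more population flag and two changed denominators, with figures that may be slightly less favourable. Group C needs no new data collection.

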1. INTRODUCTION

1.1. Sickle Cell Disease

Sickle cell disease (SCD) is a rare hereditary blood disorder caused by a point mutation within codon 6 of the β -globin gene that results in the production of an abnormal β^{E6V} -globin (β^S -globin) (INGRAM 1957). The most frequent and severe SCD phenotype, also known as sickle cell anemia, results when 2 copies of the β^S -globin gene (β^S) are present (homozygous β^S genotype, β^S/β^S). Compound heterozygosity with certain other mutations in the β -globin gene (e.g., β^S/β^C (SC genotype) or β^S/β^0 genotypes, where a β^0 mutation does not produce a β -globin [S β -thalassemia genotype]), can produce an SCD spectrum that may be as phenotypically severe as that typically associated with β^S/β^S SCD.

Worldwide, neonatal screening indicates that the number of newborns with SCD is approximately 400,000 annually, with 312,000 being of the β^S/β^S genotype, mostly in sub-Saharan Africa and India (Piel et al. 2013). The US Centers for Disease Control and Prevention estimates SCD to affect 90,000 to 100,000 persons in the US (Centers for Disease Control and Prevention, <http://www.cdc.gov/ncbddd/sicklecell/data.html>). While SCD is relatively rare in the US and Europe, it represents a significant public health burden, given the intensive management needed to improve survival and care for affected patients. From 1989 to 1993, an average of 75,000 hospitalizations due to SCD occurred in the US (Centers for Disease Control and Prevention).

Sickle cell disease is associated with significant morbidity and mortality, particularly in developing countries where it is most prevalent. Mortality in Africa is high, with the most vulnerable period being under 5 years of age (Makani et al. 2011), mainly due to bacterial infections associated with the early loss of splenic function resulting from splenic damage from sickle cells. In the US and Europe, neonatal diagnosis, early penicillin prophylaxis, extended vaccinations, and comprehensive care have improved health outcomes and survival during childhood (Quinn et al. 2010; Colombatti et al. 2016).

β^S -globin causes hemoglobin S (HbS) to form rigid polymers upon deoxygenation or other stress, e.g., dehydration, fever, etc. In turn, the intracellular formation of HbS polymers results in deformation of the red blood cell (RBC) into the characteristic sickle shape that decreases its flexibility and is responsible for chronic hemolytic anemia and acute microvascular vaso-occlusions or infarctions, resulting in acute life-threatening conditions, chronic multiple organ damage and premature death (Madigan and Malik 2006). Moreover, systemic endothelial dysfunction develops related to a decrease in nitric oxide bioavailability due to hemolysis, reactive oxygen species production, and intravascular inflammation (Morris et al. 2000, 2005; Aslan et al. 2001; Reiter et al. 2002; Gladwin et al. 2003; Reiter and Gladwin 2003; Dubert et al. 2017). The individual baseline rate of hemolysis is stable over time (Taylor et al. 2008). While a single point mutation leading to the production of HbS is the primary source of clinical complications in SCD, the presentation of the disease is heterogeneous. Severely affected patients may experience diverse complications such as severe anemia, repeated acute painful vaso-occlusive events (VOEs) due to small-vessel obstruction (vaso-occlusive crises [VOCs]; sickle cell crises), acute chest syndrome (ACS; acute event with pneumonia-like symptoms), cerebral vasculopathy, and chronic organ damage that may involve the bones, kidneys, heart, liver, and lungs or result in severe infectious complications related to functional hyposplenism.

The need for intensive therapies, including transfusions, and frequent hospitalizations greatly impairs activities of daily living and quality of life. Most patients experience painful, chronic symptoms due to recurrent underlying crises and potentially chronic complications such as bone and joint damage and ulcers. The burden of the disease increases with age and is associated with early mortality.

Cerebro-vascular accidents are a common cause of neurological injury. The chance of having a cerebro-vascular accident by 20 years of age was estimated at 11% for β^S/β^S SCD patients (O'hene-Frempong et al. 1998). Although early transcranial Doppler (TCD) screening and intensification therapy allowed the reduction of stroke risk by age 18 to 1.9% in a recent study, the cumulative cerebral risk (including stroke, abnormal TCD, stenosis, and silent strokes) remains high at approximately 50% by age 14 (Bernaudin et al. 2011). Both silent cerebral infarcts and overt stroke are associated with lower cognitive functioning (Armstrong et al. 1996). Although stroke is the major cause of morbidity in patients with SCD, ACS is the major cause of mortality in these patients. In the cooperative study of SCD (CSSCD), patients older than 20 years of age with an episode of ACS had lower survival compared to SCD patients without an episode of ACS (Castro et al. 1994).

Two overlapping subphenotypes of SCD have been proposed (Kato et al. 2007): the “hyperviscosity” subphenotype with higher hemoglobin (Hb) levels and a higher prevalence of vaso-occlusive pain crises, ACS, and osteonecrosis, and the “hyperhemolysis-endothelial dysfunction” subphenotype, in which patients have a pattern of low Hb levels and higher levels of hemolysis markers, such as reticulocyte count, serum lactate dehydrogenase (LDH), and bilirubin, as well as a higher prevalence of pulmonary hypertension, stroke, leg ulcers and priapism.

Management of SCD entails a number of approaches, including prevention and treatment of infection, pain management and transfusion therapy. Specific treatment for SCD is limited to chronic blood transfusions, Endari (L-glutamine), Droxia or Siklos (hydroxyurea; referred to as HU), Adakveo (crizanlizumab-tmca), Oxbryta (voxeletor), and allogeneic hematopoietic stem cell (HSC) transplantation (HSCT), which to date has been the only curative treatment.

Chronic blood transfusion therapy to maintain HbS below 30% significantly reduces the risk of recurrent stroke and decreases the incidence of associated co-morbidities but leads to allo-immunization or delayed hemolysis transfusion reactions in approximately 30% of transfused SCD patients compared to 2 to 5% of all transfusion recipients. Thus, continued transfusions are problematic and may lead to life-threatening complications (Friedman et al. 1996; Meunier et al. 2008; Campbell-Lee and Kittles 2014). Iron overload is often a major issue in SCD patients on chronic transfusion therapy, with ensuing long-term liver complications and the need for iron chelation therapy (de Montalembert et al. 2017). In addition, chronic active hepatitis and resultant hepatic failure is a significant complication of transfusion therapy. As many as 11% to 20% of patients with SCD on chronic transfusion regimens are infected with hepatitis C virus (HCV) (DeVault et al. 1994; Arlet et al. 2016).

L-glutamine oral powder (Endari) is approved in the US (Endari PI, 2017) for use in reducing the acute complications of SCD in adults and pediatric patients ≥ 5 years of age. In May 2019, the Committee of Medicinal Products for Human Use (CHMP) in the European Union (EU) issued a negative opinion for Xyndari (brand name in EU) stating that the data in the marketing

authorization application did not show that the drug was effective at reducing the number of SCD crises or hospital visits.

Hydroxyurea (HU) has been helpful in a subset of patients only, with response rates of approximately 40% to 50% ([Ma et al. 2007](#)). Patients who respond show a decrease in the rate of pain and ACS events ([Charache et al. 1995](#); [Steinberg et al. 1997](#)), and beneficial findings in other organs have also been reported ([Hankins et al. 2008](#)). Hydroxyurea is a well-tolerated medication with few significant short-term toxicities; e.g., transient and reversible myelotoxicity, occasional gastrointestinal discomfort, nail or skin hyperpigmentation, and skin ulceration. However, HU is a chemotherapeutic drug; and given its primary mechanism of action and in vitro reports as a clastogen, mutagen, teratogen and carcinogen, the long-term safety profile of HU treatment in SCD remains an ongoing concern ([McGann and Ware 2011](#)). Although most studies to date have confirmed the beneficial role of HU in preventing VOEs and ACS in all age groups, the inferiority of HU in patients with stroke and chronic transfusions has been established ([Ware and Helms 2012](#)). Importantly, HU is a palliative, but not a curative, treatment modality, and studies assessing the utilization of HU in patients with SCD have identified patient compliance as a barrier to its use and efficacy ([Brandow and Panepinto 2010](#)). While there is some non-randomized evidence that patients treated with HU may live longer than those not treated with HU, patients treated with HU still experience SCD complications and, unfortunately, still die of their disease ([Bakanay et al. 2005](#); [Voskaridou et al. 2010](#)).

Adakveo (crizanlizumab) is a humanized IgG2 kappa monoclonal antibody against P-selectin that blocks interactions between endothelial cells, platelets, red blood cells, and leukocytes. It is indicated to reduce the frequency of VOCs in adults and pediatric patients aged 16 years and older with SCD ([Adakveo PI, 2019](#)). Adakveo does not impact the pathophysiological basis of the disease but is designed to reduce a specific symptom of the disease, namely pain due to vaso-occlusive disease. Efficacy was evaluated in the pivotal study and Adakveo demonstrated a lower median annual rate of VOC compared to placebo (1.63 versus 2.98); however, VOC often persisted despite treatment. Thus, it could not be considered a potentially curative therapy and symptoms often persist despite treatment.

Oxbryta (voxelotor) is a hemoglobin S polymerization inhibitor indicated for the treatment of SCD in adults and pediatric patients 12 years of age and older. In clinical trials, Oxbryta treatment led to an increase in total hemoglobin of approximately 1 g/dL ([Oxbryta PI, 2019](#)). However, subjects who were receiving chronic packed red blood cell (pRBC) transfusions were excluded from these studies. Importantly, treatment with Oxbryta did not demonstrate any difference in annualized vaso-occlusive events nor did it show any improvement in patient-reported outcomes. Thus, severely affected patients who can experience acute, painful and quantifiable VOEs may not benefit from this treatment given no notable reductions in VOC/ACS events were observed in Oxbryta clinical trials.

Allogeneic hematopoietic stem cell transplantation is currently the only available curative treatment for patients with SCD, and is indicated for pediatric patients with an HLA-matched sibling donor who have severe clinical symptoms such as clinically overt stroke, frequent VOEs, and ACS while on HU ([Fitzhugh et al. 2014](#)), where organ damage has been documented and reduced lifespan is expected. Unfortunately, only approximately 14% of patients have a suitable, sibling, human leukocyte antigen (HLA)-matched donor, and identifying a matched donor is a major barrier to allogeneic HSCT ([Vermylen 2003](#)). Furthermore, allogeneic HSCT is associated

with 5 to 20% mortality, in large part due to complications from graft-versus-host-disease (GVHD) (Lucarelli et al. 1993; Locatelli et al. 2003; Vermeylen 2003).

Allogeneic hematopoietic stem cell transplantation involves a conditioning regimen to eradicate existing HSCs to allow for successful engraftment of subsequently infused allo-HSCs.

Specific inclusion and exclusion criteria to maximize success rates and minimize risks of the procedure are now well established (Bernaudin et al. 2007; Walters et al. 2010). Allogeneic hematopoietic stem cell transplantation outcomes are generally better when performed earlier in life (Kamani et al. 2011). In a recent study of 1000 patients with SCD who received allo-HSCT from an HLA-matched sibling donor, 5-year probabilities of overall survival (OS) and event-free survival (EFS) were 92.9% and 91.4%, respectively. The 5-year OS was 95% and 81% for patients younger than 16 years and those aged 16 years or older respectively; the corresponding EFS was 93% and 81% (Gluckman et al. 2017).

The use of intra-familial, partially matched donors or matched, unrelated donors presents a safety risk to patients, and is infrequently employed for SCD. Additional donor sources and modifications to allo-HSCT are being investigated but are currently limited to experienced centers and clinical trials (Bolaños-Meade et al. 2012; Hsieh et al. 2014; Shenoy et al. 2016; Allen et al. 2017). In the context of SCD, an international expert panel has recommended that allo-HSCT should only be offered using a myeloablative conditioning regimen and only to young symptomatic patients with available matched-sibling donors (MSDs) (Angelucci et al. 2014). The absence of suitable donors, the significant risks of transplantation, and the requirement for post-transplant immunosuppression indicate unmet medical needs, even with allogeneic HSCT, for SCD patients.

1.2. bb1111

bb1111 (lovotibeglogene autotemcel, also known as LentiGlobin BB305 Drug Product for SCD) is an autologous CD34+ cell-enriched population from patients with sickle cell disease that contains HSCs transduced with BB305 lentiviral vector encoding the $\beta^{\text{A-T87Q}}$ -globin gene. Expression of $\beta^{\text{A-T87Q}}$ -globin is driven by the erythroid lineage-specific globin locus control region (LCR). $\beta^{\text{A-T87Q}}$ -globin is a single amino acid variant of β -globin that conserves the protein's function while allowing for quantification relative to other globin species. Additionally, $\beta^{\text{A-T87Q}}$ -globin has anti-sickling properties because the amino acid change from threonine to glutamine at position 87 sterically inhibits the polymerization of Hb chains.

After undergoing myeloablation, subjects receive bb1111 via intravenous (IV) infusion, leading to peripheral reconstitution with corrected erythrocytes. As bb1111 consists of genetically modified autologous cells, there is no risk of GVHD.

Extensive nonclinical studies have demonstrated that transfer of the human $\beta^{\text{A-T87Q}}$ -globin gene under the control of the β -globin promoter and enhancer elements of the β -globin locus control region (LCR) into HSCs by means of LVVs reliably results in long-term correction of SCD in relevant mouse models (Pawliuk et al. 2001). Similarly, effective ex vivo $\beta^{\text{A-T87Q}}$ -globin gene transfer into human CD34+ HSCs was observed (Imren et al. 2004) (see the Investigator's Brochure).

